Sixty patients suffering from post-mastectomy shoulder dysfunction will be randomly divided into two equal groups (Group A and Group B) each one has 30 patients. Patients' age will range from 40 to 55 years.

2. Equipment and tools:

2.1. Measurement equipment:

- Hand-held dynamometer: for measurement of muscle strength (Mañago et al., 2017).
- Digital inclinometer: for measurement of shoulder flexion, abduction and scapular upward rotation (An et al., 2021).
- Shoulder Pain and Disability Index (SPADI): for measurement of shoulder disability (Alsanawi et al., 2015).

2.2. Therapeutic procedures:

- Motor control retraining exercises of the scapular musculature.
- Traditional physical therapy.

Hypothesis:

It will be hypothesized that:

Motor control retraining exercises have no effect on shoulder dysfunction postmastectomy.

Basic Assumptions:

It will be assumed that:

- All patients will continue in the study.
- All patients will follow the instructions during the treatment.
- All patients are free from any chronic impairment.
- The clinical method of measurement will be reliable and valid.

Definitions of terms:

The following terms will be defined for the clear understanding of the terminology that will be used in the present study:

Mastectomy:

Mastectomy is a procedure consisting of invasive breast removal due to some anatomical and functional changes previously diagnosed. Surgical treatment ranges from lumpectomy to mastectomy, with or without removal of axillary lymph nodes (Basilio et al., 2014).

Motor control:

Motor control is defined as the ability of the nervous system to control posture and movement for a given motor task and encompasses all the motor, sensory and integrative processes associated with the planning and execution of the task (van Dieën et al., 2018).

Shoulder Pain and Disability Index (SPADI):

The SPADI is a self-administered questionnaire that contains thirteen items which assess two domains (pain and disability) (Shamley et al., 2012). It has an

8-item subscale to evaluate disability and a 5-item subscale to measure pain. Each subscale is summed and transformed to a score out of 100. A mean is taken of the two subscales to give a total score out of 100, higher score indicating greater impairment or disability (Breckenridge and McAuley, 2011). The Arabic version of SPADI has excellent validity and reliability (Alsanawi et al., 2015) Instrumented digital hand-held dynamometer:

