- 2. Manual therapy techniques commonly used in clinical practice to manage symptoms, e.g. used to lengthen tight muscles or reduce active trigger point pain presentations.

3.3. physiological effect:

Improper control is characterized by changes in muscle activation levels. More specifically, lower activity of the serratus anterior, higher activity of the upper and lower trapezius, and lack of coordination between the different parts of the trapezius have been observed. This inadequate muscle control is believed to contribute to a reduction of amplitude in posterior tilting and lateral rotation of the scapula during arm elevation. Lower activity of the infraspinatus and subscapularis as well as inadequate coactivation of the scapulohumeral muscles have also been reported. This abnormal muscle control is most likely associated with a reduction of the subacromial space leading to impingement (Hawkes et al., 2019).

Motor control include production of reflexive, automatic, adaptive and voluntary movements and the performance of efficient, coordinated, goal-directed movement patterns which involves multiple body systems (input, output, and central processing). Evidence suggests exercise program mainly focusing on motor control principle for the scapulothoracic joint has been a promising treatment option for shoulder impingement (Hara, 2020).

CHAPTER III

SUBJECTS, MATERIALS AND METHODS

In this part of the study, the materials and methods will be presented under the following headings: subjects, equipment, procedures of the study and the statistical procedures.

1-Subjects:

1.1.Sample size:

Sample size calculation was done using, shoulder function as reported in (Mohite and Kanase, 2014), with 90% power at $\alpha = 0.05$ level, number of measurements 2, for 2 groups and effect size = 0.45 using F-test MANOVA repeated measures within and between interaction. The minimum proper sample size is 54 subjects, adding 6 (11%) subjects as drop out, so total sample size is 60 subjects 30 in each group. The sample size was calculated using the G*Power software (version 3.0.10) (figure 2).

[figure not shown]

Figure (2): sample size calculation

sixty patients suffering from post-mastectomy shoulder dysfunction will participate in this study. Their ages will range from 40 to 55 years. The participants will be selected from Cairo university hospitals.

1.2. Design of the study:

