Hand-held dynamometry (Lafayette manual muscle tester) will be used to measure isometric strength of shoulder flexion and abduction. It is an ergonomic hand-held device for objectively providing reliable, accurate readings that conform to most manual muscle testing protocols. It has good to excellent validity and reliability for most measures of isometric muscle strength particularly for proximal muscle groups. It has a large, easy-to-read LCD screen that displays results in both pounds and kilograms. It also has a weight capacity of up to 300 lbs. (mentiplay et al., 2015). Fig. (3).

Fig. (3) Lafayette hand-held dynamometer

2.1.c- Digital inclinometer:

A digital inclinometer is used to measure shoulder flexion, abduction and upward rotation of scapula. It has digital screen that display the angle at which the inclinometer is situated allowing direct joint angle measurements (An et al., 2021).

2.2. Therapeutic Equipment and Tools:

Motor control retraining exercises for scapular muscles.

3-Procedures of the study:

3.1. Measurement procedures:

3.1.a. The Shoulder Pain and Disability Index (SPADI):

To answer the questions, the patient is instructed to place a mark on the 100mm straight line, this line represents a continuum between "no pain" (zero) and "the worst pain that the patient could feel" (ten) for pain dimension and "no difficulty" (zero) and "so difficult it requires help" (ten) for the disability dimension, respectively. To calculate a final percentage score for assessing shoulder

dysfunction, a mean is taken of the two subscales to give a total score out of 100, higher score indicating greater impairment or disability (**Brindisino et al., 2021**). The Arabic version of SPADI has excellent validity and reliability (**Alsanawi et al., 2015**)

3.1.b- Instrumented digital hand-held dynamometer:

A handheld dynamometer will be used to assess maximal strength pre-treatment and post treatment. Maximal strength tests for shoulder flexion and abduction will be measured. When applying the manual resistance for each test the handheld dynamometer is used to obtain force measures. Two trials were performed for each shoulder motion (Scibek and Carcia, 2012).

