Each test consisted of the subject maximally contracting against the external force until this external force, applied by the tester, caused a "break" in the test position of the subject. The force required to break the test position was then recorded as the relative strength of the specific muscle (Scibek and Carcia, 2012). Fig. (5)

Fig. (5)

3.1.c- Digital inclinometer:

Digital inclinometer provides a real-time digital reading of angles with respect to either a horizontal or vertical reference (An et al., 2021).

Scapular upward rotation will be measured with subjects in the resting position and then with the shoulder elevated to 60 and 120 in the scapular plane. The angle

between the scapular spine root and posterolateral acromion will be measured in the resting position and with the shoulder joint elevated 60 and 120 Scapular upward rotation will be measured similarly (An et al., 2021). Fig. (6)

fig. (6)

Shoulder flexion ROM will be measured with the patient elevating the arm as high as possible in the sagittal plane without any extension of the spine (Clausen et al., 2017). Fig. (7a)

Shoulder Abduction ROM will be measured with the patient elevating the arm as high as possible in the frontal plane without lateral flexion of the spine (Clausen et al., 2017). Fig. (7b)

[figure not shown]

Fig. (7)

3.2. Therapeutic procedures:

3.2.a- Motor control retraining exercises:

The motor control retraining package was targeted at correcting movement impairments of the scapula by re-educating muscle recruitment. There were two components to the package: (Worsley et al., 2013).

- 1. Motor control exercises to correct alignment and coordination, which involve a) learning optimal scapular orientation at rest and then controlling optimal orientation during active arm movements; b) muscle specific exercises for trapezius and serratus anterior
- 2. Manual therapy techniques commonly used in clinical practice to manage symptoms, as trigger point therapy and pectoralis minor supine manual stretch will be performed as necessary.

During the motor control exercises, scapular position is optimised in relation to the thorax, initially by being altered manually by the therapist on a subject specific basis. This involved the therapist using observation and palpation to alter orientation/alignment of the scapula and clavicle using the following guidelines (Worsley et al., 2013).

- Acromion should be higher than the superior medial border of scapula.

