traction and oscillating movements and provide early motion of joint structures and synovial fluid. No weight will be used initially. When the patient will tolerate stretching, a weight will be added to the hand or as wrist cuffs to cause further distraction force. To direct the stretch force to glenohumeral joint, stabilize the scapula against the thorax manually or with a belt (Patel, 2022).

4.Statistical procedures:

The collected data will be statistically analysed using:

- Descriptive statistics (mean and standard deviations).
- Inferential statistics: unpaired t-test will be used to compare subjects' characteristics of the two groups.
- Repeated measures MANOVA will be used to compare all dependent variables within and between groups.
- Statistical analysis will be conducted using SPSS for Windows, version 20 (SPSS, Inc., Chicago, IL). Statistical significance will be set at the (p< 0.05).

References

Alsanawi, H. A., Alghadir, A., Anwer, S., Roach, K. E., and Alawaji, A. (2015). Cross-cultural adaptation and psychometric properties of an Arabic version of the Shoulder Pain and Disability Index. *International journal of rehabilitation research*. *Internationale Zeitschrift fur Rehabilitationsforschung*. *Revue internationale de recherches de readaptation*, 38(3): 270–275.

An, D. I., Park, J. E., Lee, C. H., & Kim, S. Y. (2021). Reliability of scapular upward rotation and anterior-posterior tilt measurements using a modified digital inclinometer in patients with subacromial impingement syndrome. *Journal of Back and Musculoskeletal Rehabilitation*, 34(5), 837-843.

Bae, Y. H., Lee, G. C., Shin, W. S., Kim, T. H., & Lee, S. M. (2011). Effect of motor control and strengthening exercises on pain, function, strength and the range of motion of patients with shoulder impingement syndrome. Journal of Physical Therapy Science, 23(4), 687-692.

Bakhsh W., and Nicandri G. (2018): "Anatomy and physical examination of the shoulder". Sports medicine and arthroscopy review; 26(3): e10-e22.

Borstad J. D., and Szucs K. A. (2012): "Three-dimensional scapula kinematics and shoulder function examined before and after surgical treatment for breast cancer". Human movement science; 31(2): 408-418.

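### The 90% power at 54 patients belongs to a test on one outcome, but the analysis covers six to eight outcomes at p<0.05 and none is named primary

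*Protocol*

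**What the plan says.** Chapter III, section 1.1 (Sample size) bases the calculation on a single outcome from a cited study: "Sample size calculation was done using, shoulder function as reported in". The settings are 90% power, alpha 0.05 and "number of measurements 2, for 2 groups and effect size = 0.45 using F-test MANOVA repeated measures within and between interaction". The result is a minimum of 54, plus 6 for dropout, giving 60 (30 per group). The two measurements are the two time points in section 2.1, before treatment and after 8 weeks. They are not two outcomes.

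Section 4 (Statistical procedures) sets the analysis: "Repeated measures MANOVA will be used to compare all dependent variables within and between groups". The criterion is "Statistical significance will be set at the (p< 0.05".

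The outcomes are spread over several sections:

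- Delimitations, 2.1: "Shoulder Pain and Disability Index (SPADI): for measurement of shoulder disability".
- Chapter III, 2.1.c: "A digital inclinometer is used to measure shoulder flexion, abduction and upward rotation of scapula".
- Chapter III, 3.1.b: "Maximal strength tests for shoulder flexion and abduction will be measured".
- Chapter III, 3.1.c: scapular upward rotation is "measured with subjects in the resting position and then with the shoulder elevated to 60 and 120 in the scapular plane".

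The protocol labels no outcome primary or secondary. Section 1.1 does not say which instrument measures the shoulder function it was sized on.

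**The concern.** The power statement and the analysis statement describe different tests. Section 1.1 supports a test of one outcome. Section 4 specifies an analysis of all of them, and can be read in two ways with different consequences.

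- **One joint multivariate test.** Its 5% level holds for the overall test, but the power in section 1.1 was not calculated for it. The joint test could miss a SPADI benefit of the size the trial was planned to detect.
- **The same test repeated for each variable.** Each test keeps 90% power if its own effect is 0.45, but the 5% error rate does not hold across the set. With no primary outcome, any one significant result out of six to eight could be reported as the effect on shoulder dysfunction, which is the trial's stated question.

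These are alternatives, not two faults at once. On either reading, one of the two stated rates is not secured for the trial's conclusion.

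**Working it through.** **Inputs from the protocol.** Effect size 0.45, alpha 0.05, power 90%, 2 groups, 2 time points, minimum N = 54, planned N = 60 (section 1.1); all outcomes analysed at p<0.05 (section 4).

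**Count of outcomes (mine; the protocol gives none).** SPADI total 1, strength 2, range of motion 2, scapular upward rotation 1 or 3. That makes 6 or 8.

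**Step 1: reproduce the plan's figure.** I take 0.45 as the effect size f(V) of G*Power. For one outcome, the group-by-time F test has df1 = (2−1)(2−1) = 1, df2 = N−2 and noncentrality λ = N × 0.45² = 0.2025N.

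- N = 53: λ = 10.73, power 0.895.
- N = 54: λ = 10.935, df 1 and 52, power 0.9006.
- N = 60: λ = 12.15, power 0.929.

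The minimum is 54, as stated, with df1 = 1, so this is a one-outcome calculation. In this design f = 0.45 equals a between-group difference in change of 0.9 SD, because λ = (N/4) × 0.9² = 0.2025N.

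**Step 2: one joint test on p outcomes.** Here df1 = p, df2 = N−2−p+1 and λ = (N/4) d′R⁻¹d, where d holds the standardised differences in change and R is the correlation matrix of the change scores. The protocol gives neither d nor R. I assume 0.9 SD on SPADI and a common correlation r.

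The lowest power arises when the other outcomes add no separation, so that λ stays at 0.2025N:

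| Outcomes | N = 54 | N = 60 |
|---|---|---|
| 6 | 0.623 | 0.685 |
| 8 | 0.549 | 0.614 |

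For eight outcomes at N = 54 (df 8 and 45), under three assumptions about the other seven:

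| Other outcomes move by | r = 0.3 | r = 0.5 | r = 0.7 |
|---|---|---|---|
| 0 SD | 0.683 | 0.842 | 0.980 |
| 0.45 SD | 0.612 | 0.549 | 0.626 |
| 0.9 SD | 0.960 | 0.842 | 0.709 |

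For six outcomes at N = 54 and the same three values of r, power is 0.741, 0.879 and 0.987 if the others do not move, and 0.968, 0.879 and 0.770 if all move 0.9 SD.

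**Step 3: one test per outcome at 0.05.** With independent outcomes and no true effect, the chance of at least one false positive is 1 − 0.95⁸ = 0.337 for eight and 1 − 0.95⁶ = 0.265 for six. With correlated outcomes (simulated, 80,000 trials, 27 per arm):

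| Outcomes | r = 0.3 | r = 0.5 | r = 0.7 |
|---|---|---|---|
| 6 | 0.245 | 0.207 | 0.167 |
| 8 | 0.301 | 0.253 | 0.194 |

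A separate simulation for eight outcomes gave 0.300, 0.250 and 0.191.

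**The case against.** The best defence is that sizing on one outcome and analysing several is ordinary practice. Section 1.1 already says the calculation used shoulder function, so it does not literally claim 90% power for anything else. The choice between a joint model and separate models, and any multiplicity adjustment, may sit in an analysis plan that is not shown. That is fair for those details. It does not cover the primary outcome, which belongs in the protocol beside the power claim that depends on it.

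The second defence is that the joint-power figures rest on assumptions. This stands. A common correlation is a crude description when three of the eight variables are one measure at three arm positions, and lower correlations can help: at r = 0.1, eight outcomes and N = 54, power is 0.831 if the others move 0.45 SD and over 0.99 if all move 0.9 SD. The figures therefore show that joint power is undetermined. They do not show that it is low.

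Third, the protocol does not tie shoulder function to SPADI, and the cited source is not at hand. The link is an inference. It is a reasonable one: SPADI is the only function or disability score listed, and Chapter III, section 3.1.a uses its total to assess shoulder dysfunction. The sponsor should still confirm it.

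**Conclusion.** The concern holds. The sample size of 54 is correct for one outcome, but the analysis in section 4 is not tied to that outcome. If section 4 means one joint test, 90% power is not established. With eight outcomes at N = 54, power has a floor of 0.549 and exceeds 0.95 in favourable cases, given 0.9 SD on SPADI and the assumed correlations. Enrolling and retaining all 60 raises the floor only to 0.614. If section 4 means separate tests, the family-wise error is 26% (six) to 34% (eight) under independence, and about 17% to 30% at assumed correlations of 0.7 to 0.3. The mismatch and the missing primary outcome are certain from the text. The sizes depend on my count of outcomes and on effects and correlations that the protocol does not give. This should be fixed before analysis, but it does not call the number of patients into question.

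**What to change.** - **Section 4:** name SPADI total at 8 weeks as the single primary outcome, test its group-by-time effect alone at two-sided 0.05, and label strength, range of motion and scapular rotation as secondary.
- **Section 1.1:** state that 90% power at N = 54 applies only to that test, and confirm that SPADI total is the shoulder function measure on which the trial was sized.

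With this change 54 stands as calculated. The cost is two sentences and no extra patients. The price is that claims on strength, range of motion and scapular rotation become secondary.

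If a joint MANOVA is kept as the main test, the 90% claim should be withdrawn for it or recomputed with stated effects and correlations for every variable. Keeping all eight outcomes confirmatory would cost more. With a Bonferroni level of 0.05/8 = 0.00625 and f = 0.45 for each, power per outcome is 0.675 at N = 54 and 0.739 at N = 60, and 90% needs 84 evaluable patients, or 94 enrolled at 10% dropout (84/0.9 = 93.3, rounded up).

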Normal pain free motion of the arm and shoulder requires mobility in the scapula-thoracic, glenohumeral, acromioclavicular and sternoclavicular joints. Under healthy conditions elevation of the arm is accompanied by scapula retraction, lateral rotation and posterior tilt. However, when scapula-thoracic motion is disproportionate to glenohumeral motion, the potential exists for microtrauma and long-term pain (**Trundle et al., 2014**).

Motor control retraining refers to neuromuscular control of the body (trunk and limbs) in static postures and functional tasks using the process of initiating, directing, and grading purposeful voluntary movement. It's necessary for the optimization of upper limb movement patterns, which helps the load spread evenly among multiple movement system components. The presence of uncontrolled movement may cause tissue overload that in turn can lead to pain, damage, and various musculoskeletal conditions. (Śliwiński et al., 2021).

Statement of the problem:

Do motor control retraining exercises have an effect on shoulder dysfunction post-mastectomy?

Purpose of the study:

The purpose of the study is to evaluate the effect of motor control retraining exercises on shoulder dysfunction post mastectomy.

Significance of the study:

The GH joint significantly depends on muscle control and mid-range stability. To guarantee that functional tasks is performed normally, Glenohumeral and scapulothoracic motions must interact and coordinate during arm raising to prevent the humerus head from striking the coracoacromial arch and seriously jeopardizing the soft tissue tissues around the shoulder from impingement. (Neto et al., 2018).

Motor control and strengthening exercises can improve function in shoulder impingement patients by realigning the scapula and changing muscle recruitment patterns. Peripheral musculoskeletal impairments can be associated with cortical reorganisation. Movement retraining using the principles of motor control retrain muscle recruitment patterns and improve scapular kinematics, reducing subacromial impingement, thus improving function and reducing pain (Worsley et al., 2013).

Furthermore, the need of this study is developed from the lack in the quantitative knowledge and information in the published studies about the effect of motor control retraining exercises on shoulder dysfunction post-mastectomy.

Delimitations:

This study will be delimited in the following aspects:

1.Subjects:

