As shown in figure (1), A complex network of muscular anatomy provides multiple functions of the shoulder. Rotator cuff muscles constitute of the supraspinatus, infraspinatus, teres minor, and subscapularis. These muscles allow

synergistic co-contraction to guide movement and anchor the scapula (Bakhsh and Nicandri, 2018). Fig. (1)

[figure not shown]

Fig. (1): Muscles and Fascia of the Shoulder (Adopted from Lam and Bordoni, 2021).

There are numerous muscles attached to the scapula. The trapezius, the levator scapulae, the rhomboids, the serratus anterior, the pectoralis minor and the subclavius muscles achieve significant contribution to scapulothoracic motion. The serratus anterior supports the medial angle against the chest wall, and the trapezius rotates and elevates the scapula in synchronization with glenohumeral movement (**Ribeiro et al., 2016**).

2.2. Biomechanics:

Glenohumeral joint stability is impacted by the musculature functioning far from the shoulder itself. Large torques can be generated about the shoulder joint by the action of latissimus dorsi, serratus anterior, pectoralis major, and deltoid due to their cross-sectional anatomy and distance from the joint centre of rotation (Levine and Rigby, 2018).

The scapulothoracic articulation consists of a space between the posterior surface of the thoracic rib cage and the anterior surface of the scapula. The movement of the scapula on thorax is smooth due to the neurovascular, muscular, and bursal structures (**Ribeiro et al., 2016**).

Arm raising depends on coordination between glenohumeral and scapulothoracic motions, which ensures that functional tasks can be performed without the humerus' head striking the coracoacromial arch and putting the soft tissue structures surrounding the shoulder joint at risk of impingement. Shoulder muscles, which are functionally classified as stabilizers and prime movers, make up the dynamic structures. Timed interaction between these two groups of muscles is essential to achieve a smooth and physiologic scapulohumeral rhythm (Neto et al., 2018).

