In this randomised controlled trial study (RCT), the patients will be randomly assigned into two equal groups (30 patients for each group):

1.2.a. Group A (study group):

This group will include 30 patients with post mastectomy shoulder dysfunction who will receive motor control retraining exercises in addition to their conventional physical therapy program, three sessions per week for 8 weeks, for 45:60 minutes according to patient's ability (**Bae et al.,2011**).

1.2.b. Group B (control group):

This group will include 30 patients with post mastectomy shoulder dysfunction who will receive conventional physical therapy program in the form of shoulder joint mobilization, posterior capsule stretching and shoulder range of motion exercise (ROM) (Codman's pendulum exercises) for 30 minutes according to patient's ability, three sessions per week for 8 weeks (**Duzgun et al.**, 2019; Yiasemides et al., 2011).

1.3. Criteria for the patient selection:

1.3.a -Inclusion Criteria:

The subject selection will be according to the following criteria:

- Female patients with age range between 40-55 years.
- All patients have shoulder dysfunction.
- Patients were 2 months to 4 months post modified radical mastectomy or axillary lymph node dissection.
- Patients received their radiotherapy or chemotherapy or both.

1.3.b- Exclusion Criteria:

The potential participants will be excluded if they meet one of the following criteria:

- Rheumatoid arthritis.
- History of trauma or accidental injuries.
- Neurological involvement (stroke, Parkinsonism).
- History of surgery on involved shoulder.
- Diabetic patient.
- Moderate and severe lymphoedema.

2-Tools and equipment:

2.1. Measurement tools and equipment:

All Measurements will be taken before the treatment (pre-treatment) and after 8 weeks (post-treatment).

2.1.a- Shoulder Pain and Disability Index (SPADI):

The SPADI is a self-administered questionnaire that contains thirteen items which assess two domains (pain and disability) (Shamley et al., 2012). It has an 8-item subscale to evaluate disability and a 5-item subscale to measure pain. Each subscale is summed and transformed to a score out of 100. A mean is taken of the two subscales to give a total score out of 100, higher score indicating greater impairment or disability (Breckenridge and McAuley, 2011). The Arabic version of SPADI has excellent validity and reliability (Alsanawi et al., 2015)

2.1.b- Instrumented digital hand-held dynamometer:

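### Does as-needed manual therapy and longer sessions in Group A undercut a purpose worded as the effect of motor control retraining exercises?

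*Protocol*

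**What the plan says.** In Chapter I the aim reads: "The purpose of the study is to evaluate the effect of motor control retraining exercises on shoulder dysfunction post mastectomy". The hypothesis, in null form, is: "Motor control retraining exercises have no effect on shoulder dysfunction postmastectomy". The therapeutic tools in Chapter III section 2.2 are a single line: "Motor control retraining exercises for scapular muscles".

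Chapter III section 3.2.a, headed with the same label, describes a package of two components. The first is motor control exercises: learning scapular orientation, then muscle-specific work. The second is manual therapy for symptoms: "trigger point therapy and pectoralis minor supine manual stretch will be performed as necessary". Chapter II section 3.2 gives the same two-part structure and says that the manual techniques are "used to lengthen tight muscles or reduce active trigger point pain presentations".

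Section 3.2.b, the programme for both groups, holds joint mobilization, posterior capsule stretching and pendulum exercise. Neither trigger point therapy nor the pectoralis minor stretch is in it.

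Section 1.2.a gives Group A its treatment "in addition to their conventional physical therapy program, three sessions per week for 8 weeks, for 45:60 minutes". Section 1.2.b gives Group B the conventional programme alone, "for 30 minutes according to" the patient's ability, at the same frequency and for the same 8 weeks.

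**The concern.** Read quickly, the aim is about exercises while the arms differ in three things at once: the exercises, discretionary manual therapy and therapist time. No arm isolates the exercises and contact time is not matched. The rationale under Significance of the study credits benefit to retrained muscle recruitment and does not mention manual therapy.

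There is also a plausible route from the second component to the outcomes. SPADI is self-completed and its total is the mean of a pain and a disability subscale, so pain relief by any means lowers it. Chapter II section 2.1 says that "the pectoralis minor and the subclavius muscles achieve significant contribution to scapulothoracic motion", and scapular upward rotation is measured. If the manual work or the extra time produced part of a group difference, a reader who takes the aim literally would credit all of it to the exercises. The stake is attribution. Type I error and power are not involved.

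**Working it through.** **1. The plan's own figure.** Section 1.1 gives 54 patients from effect size f = 0.45, two groups, two measurements, alpha 0.05 and power 90%, for the within-between interaction of a repeated-measures MANOVA. With df1 = (2 − 1)(2 − 1) = 1, df2 = N − 2 and noncentrality λ = N × f²:

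- N = 53: power 0.8950
- N = 54: λ = 54 × 0.2025 = 10.935, power 0.9006

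The smallest N reaching 90% is 54, as stated, and 54 + 6 = 60. The concern does not touch this figure.

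**2. Contact time.** Inputs are from sections 1.2.a and 1.2.b. Sessions: 3 × 8 = 24. All durations are nominal, since both arms' times depend on the patient's ability.

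| Reading of 45 to 60 minutes | Group A | Group B | Difference |
|---|---|---|---|
| Whole session | 24 × 45 to 60 min = 18 to 24 h | 24 × 30 min = 12 h | 6 to 12 h |
| On top of 30 min conventional | 24 × 75 to 90 min = 30 to 36 h | 12 h | 18 to 24 h |

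The text does not settle which reading is meant. Group A is longer by at least 6 h under both.

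**3. Can the manual therapy time be sized?** Take the whole-session reading and assume that the conventional part takes 30 minutes in Group A too. The package then has 15 to 30 minutes. The only timed exercise step is 2 minutes, or 3 × 2 = 6 if done in each of three planes. That leaves 15 − 6 = 9 to 30 − 2 = 28 minutes, which also have to hold teaching and the untimed muscle-specific exercise. The remainder is compatible with no manual therapy at all.

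The same subtraction in Group B gives a similar picture. Stretching takes 10 × 20 s + 9 × 30 s = 470 s, or 7.8 minutes. Mobilization takes 1 to 2 minutes, or 3 to 6 if timed per technique. That leaves 30 − 7.8 − 6 = 16.2 to 30 − 7.8 − 1 = 21.2 minutes for untimed pendulum work and set-up. Untimed minutes occur in both arms and do not measure confounding.

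**4. SPADI.** Total = (pain + disability)/2, so a 10-point change in pain alone moves the total by 5. This is an identity. The document gives no estimate of what the manual component does to pain.

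**5. The label, place by place.**

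| Place | Term used |
|---|---|
| Purpose, Hypothesis, section 1.2.a, section 2.2 | motor control retraining exercises |
| Heading of Chapter II section 3 (components in 3.2) | motor control retraining exercises |
| Heading of Chapter III section 3.2.a | motor control retraining exercises |
| First component within the package | motor control exercises |

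The aim uses the package's name, not the first component's. No two places disagree about what Group A receives.

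**The case for a change.** The strongest case for a change is that the word exercises does not naturally cover therapist-applied trigger point work. Section 3.2.a itself separates exercises from manual therapy, and the treatment lists mention no manual therapy for the study arm. If the label is shorthand, the purpose and hypothesis do not say so. Rewording would be cheap, and a record of minutes and techniques delivered could not be reliably rebuilt after the trial.

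Part of this stands. The label is imprecise, and a result reported as the effect of the exercise component alone would claim more than the comparison supports. The rest is weaker:

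- A purpose statement need not repeat a definition that the methods give under the same name.
- The treatment lists are poor evidence of exclusion. Section 2.2 leaves out conventional therapy altogether, and the list in Chapter I names headings without any components.
- Extra time comes with an add-on comparison, and the protocol states it for both arms. Matching time or isolating components would answer a different question.
- The route to the outcomes is largely inference. Chapter II section 3.2 describes what the techniques are used for, and section 2.1 is a list of muscles. Neither reports an effect on SPADI or upward rotation.
- A per-session record in both arms would mean up to 60 × 24 = 1,440 entries. It is commonly left to operational documents and changes no analysis.

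**Conclusion.** The facts are right, but they do not show a defect in the plan. The trial compares the two-component package plus conventional therapy with conventional therapy alone. Randomisation supports that comparison, and it matches the intervention as the protocol defines it. Followed as written, the plan gives a valid answer to that question, and the sample size of 54 plus 6 and the analysis stand.

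Two loose ends remain, both matters of wording. The label is broader than its words suggest, which a careful report handles by describing any difference as the effect of adding the package. Section 1.2.a also leaves open whether 45 to 60 minutes includes the conventional programme; I take no view on which reading is right. The nominal excess in Group A is 6 to 12 h on one reading and 18 to 24 h on the other. These figures describe contact time and are not a measure of bias, which cannot be derived from the document.

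The conclusion rests on reading the label as the name of the package, as its two uses as a heading support.
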